EVITA

EVAluation of cardiac magnetic resonance Imaging (MRI) in follow up assessmenT of patients with pulmonary Arterial hypertension (PAH)
Prospective cohort study of *cardiac MRI in PAH*

STATISTICAL ANALYSIS PLAN

[name] / [name]

15th of December 2020

Sponsor: Centre Hospitalier Régional Universitaire de Nancy

Identifiers: NCT02845518 **Unique Protocol ID:** PHRC-15-0210

Principal Coordinator / Central Contact Person: [name] [name]

Methodologists and statisticians: [name] & [name]

I/ General considerations:

The 2-tailed significance level will set to $p < 0.05$.

II/ Descriptive analysis

Continuous variables will be expressed as mean \pm SD or as median (25-75 percentile) as appropriate. Categorical variables will be expressed as frequencies (percentages).

III/ Analyses to respond to main objective:

The aim of the trial is to assess the sensitivity and specificity cardiac magnetic resonance imaging (cMRI) regarding the diagnosis of hemodynamic criteria for intermediate risk or high-risk status determined from right heart catheterization (RHC) measurements. There will be 3 time-points: baseline, between 3 and 6 months and 24 months.

The outcome variable will consequently be hemodynamic criteria for intermediate risk or high-risk status defined as a cardiac index (CI) $< 2.5 \text{ l/min/m}^2$ or right atrial pressure $> \text{ or } = 8 \text{ mm Hg}$. This definition is in line with the last ESC/ERS guidelines for diagnosis and treatment of pulmonary hypertension (1).

The cMRI exposition variable will be defined as a cMRI CI $< 2.5 \text{ l/min/m}^2$ or a right ventricle ejection fraction (RVEF) $< 35\%$ or an absolute decrease of 10% of RVEF at a follow-up evaluation (for the second and third time-point).

Sensitivity, specificity and their exact 95% confidence intervals will be computed using the binomial distribution.

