The morbimortality event will be defined as the composite endpoint of

- 1 Death from any cause
- 2 Lung transplantation
- 3 Atrial septostomy
- 4 Worsening of PAH defined by all three following criteria: a decrease in the 6-minute walk distance of at least 15 % from baseline (or unable to perform the test), a worsening of PAH symptoms and an unscheduled hospitalization (or an increase in the length of stay in the hospital) due to PAH

The following exposition variables will be used:

- RHC and cMRI definition used in the primary analysis
- Components of the RHC and cMRI definitions
- Additional RHC variables: stroke volume index, mean pulmonary arterial pressure, pulmonary vascular resistance, SvO_2 , pulmonary arterial compliance (stroke volume divided by pulse pressure)
- Additional cMRI variables: stroke volume index, right ventricular end-systolic volume index, right ventricular end-diastolic index, right ventricular end-systolic volume divided by stroke volume as an estimate of right ventriculo-arterial coupling
- Echocardiography variables: pericardial effusion, TAPSE $< 18 \text{ mm}$, right atrium area $= \text{ or } > 18 \text{ cm}^2$.

Proportional hazard analysis

Association between factors and time to first occurrence of events will be assessed using Cox proportional hazard regression. Both univariable and multivariable analyses will be performed. The validity of the assumptions of the Cox models will be checked: proportional hazards, log-linearity, absence of interaction and collinearity.

The adjusted analyses will be adjusted for NYHA class, 6-minute walk distance and natriuretic peptides. Additional adjustment factors found significant will also be entered in a multivariable analysis after stepwise forward-backward selection using a 0.05 threshold.

Importantly, the aforementioned RHC and MRI definitions will be first used as exposition variables.

In addition, the components of each definition and additional cMRI variables will also be used as individual exposition variables.

Associations between echocardiography variables and outcome will also be evaluated.

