Three sets of analyses will be provided. The first one will assess the association of baseline data with subsequent outcome, the second one will assess the association of 3-6 months data with subsequent and the last model will assess the association of baseline and 3-6 months data with outcome using a time-dependent Cox-model. In this time-dependant Cox model, association of baseline data will be considered until the 3-6 months data is acquired; association with outcome after the 3-6 months evaluation will be assessed using the 3-6 months data.

For each model, the predictive value will be assessed using C-index and NRI (3). In addition, changes in C-Index and NRI will also be evaluated comparing models including only covariates, including covariates and RHC data, including covariates and MRI data and including covariates, RHC and MRI data. This strategy has been used previously by our group (4).

Importantly, as sensitivity analyses,

- repeated events will be considering using a negative binomial model (5-7). This survival analysis will account for the occurrence of multiple events during the follow-up,
- the associations with the components of the composite endpoint will be assessed.

Secondary objective 3:

3) To assess the multivariable association between first morbimortality events occurrence and the above factors, identifying clinical and hemodynamic variables independently contributing to prognosis. Using the results of this analysis we plan to build a multiparameter prognostic score.

Two survival models will be used in this analysis, as mentioned above: Cox survival model (for first events) and negative binomial analysis as sensitivity analysis (accounting for repeated events).

Candidate variables for this analysis are the one mentioned for the analysis of secondary objective 1 and 2. A stepwise selection procedure will be used, retaining in the analysis only factor associated with a $p < 0.05$ with the outcome.

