Internal validation of the multivariable model and of the score which could be derived from it will be performed using the bootstrap method described by Harrell *et al* (8). Importantly, variables will be used both as dichotomized variables (using the cut-offs used in the primary objective) and as continuous variables. In case a continuous variable should be dichotomized for lack of log-linearity, the cutpoint will be validated in the same bootstrap resamples as for the model and score. In addition, optimal cutpoints will also be assessed on the continuous variables based on C-index maximization (9).

Secondary objectives 4:

4) To quantify complications due to cMRI and to RHC.

This will be mostly a descriptive analysis. The overall frequency of reported adverse events and severe adverse events will be compared between groups using the Chi-Square test (or Fisher's exact test where requested). In addition, to account for the paired nature of the data, a McNemar test will be performed.

Secondary objectives 5:

5) To determine the magnitude of better tolerability of cMRI over RHC for the patient.

Physical and psychological distress due to cMRI and RHC will be measured with questionnaires.

The comparison of the Likert-type scales of the questionnaires will be carried out using the Chi-Square test.

Secondary objective 6:

6) To create a biobank for diagnosis and prognosis purposes This study is a prospective cohort study. PAH patients will be recruited in 20 centers of the French network of severe pulmonary hypertension.

Blood samples to obtain DNA at one visit from circulating blood cells and plasma at all visits with MRI.

References

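### For the secondary objective 3 prognostic model, dichotomisation is the only remedy the SAP names when a continuous predictor fails log-linearity; no transformation or spline is provided

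*SAP*

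**What the plan says.** Under *Proportional hazard analysis* in section IV, the SAP states: "The validity of the assumptions of the Cox models will be checked: proportional hazards, log-linearity, absence of interaction and collinearity". It does not say there what follows if log-linearity fails.

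Under *Secondary objective 3* the aim is a score: "Using the results of this analysis we plan to build a multiparameter prognostic score". Candidates are selected stepwise at 0.05. The rules on functional form follow:

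- Validation: "Internal validation of the multivariable model and of the score which could be derived from it will be performed using the bootstrap method".
- Form of the predictors: "variables will be used both as dichotomized variables (using the cut-offs used in the primary objective) and as continuous variables".
- Failed log-linearity: "In case a continuous variable should be dichotomized for lack of log-linearity, the cutpoint will be validated in the same bootstrap resamples", meaning the resamples used for the model and score.
- Further cutpoints: "optimal cutpoints will also be assessed on the continuous variables based on C-index maximization".

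The SAP mentions no logarithm or other transformation, no polynomial and no spline.

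**The concern.** An analyst who finds that a continuous predictor departs from log-linearity has one named option, which is to split it in two. That replaces a curve with a single step and assumes constant risk on each side. Differences within each group no longer count, and a risk that rises at both ends cannot be represented.

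The continuous use that runs alongside does not solve this. With no non-linear form specified it is a linear term, and that is the term the check has just rejected.

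At stake are the fit and discrimination of the score. Stepwise selection is also affected: a predictor whose effect is flattened by a cut may miss the 0.05 threshold and drop out.

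**Working it through.** The SAP gives no sample size, event count or effect size for this model, so there is no figure of its own to reproduce. All inputs below are assumptions that illustrate size.

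**1. Information kept by one cut.** For a standard normal predictor with a small linear effect on the log hazard, a cut at quantile q (value c) keeps a fraction φ(c)² / [q(1 − q)] of the information, where φ is the normal density.

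| Cut at | φ(c) | Calculation | Kept |
|---|---|---|---|
| Median | 0.399 | 0.399² / 0.25 | 64% |
| 75th percentile | 0.318 | 0.318² / 0.1875 | 54% |
| 90th percentile | 0.175 | 0.175² / 0.09 | 34% |

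**2. C-index in a large sample, monotone effect.** Inputs: N = 100,000, exponential survival, censoring at 2 years, about 34 to 38% events, effect linear on the log scale.

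| Hazard ratio per SD | Continuous | Median cut | Best cut (50th–60th percentile) | Loss |
|---|---|---|---|---|
| 1.5 | 0.61 | 0.58 | 0.58 | 0.61 − 0.58 = 0.03 |
| 2.7 | 0.74 | 0.67 | 0.68 | 0.74 − 0.67 = 0.07; 0.74 − 0.68 = 0.06 |

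A well-placed cut therefore costs about 0.03 to 0.07. The C-index depends only on ranks, so for one monotone predictor the raw and log-transformed versions give the same value (0.61 and 0.61; 0.74 and 0.74). The table compares cut with continuous. It does not show a gain from transforming over a linear term.

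**3. C-index at a modest sample size.** Inputs: 200 simulated data sets per shape, N = 200, about 35% events by 2 years, one standard normal predictor x. The best cut is the best-fitting of 17 between the 10th and 90th percentiles. The spline is a restricted cubic spline with 4 knots. The C-index is taken in 1,000 new subjects per run.

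| Log-hazard shape | Median cut | Best cut | Spline | True form |
|---|---|---|---|---|
| Linear, 0.5x | 0.595 | 0.581 | 0.630 | 0.635 |
| Monotone curved, ln(1 + e^(2x)) / 1.5 | 0.628 | 0.628 | 0.688 | 0.692 |
| U-shaped, 0.5x² (x² capped at 6) | 0.501 | 0.559 | 0.659 | 0.662 |

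- Monotone curved: 0.688 − 0.628 = 0.060 lost with either cut.
- U-shaped: 0.659 − 0.559 = 0.100 lost with the best cut, and 0.659 − 0.501 = 0.158 with the median cut.
- Power in the U-shaped case was 6.5% for the median cut, close to the 5% level, and about 100% for the spline tested on 3 degrees of freedom.

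The out-of-sample comparison already charges the spline for its extra degrees of freedom.

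**4. What the bootstrap does.** Repeating the cutpoint choice in each resample estimates how far apparent performance exceeds true performance and shows how unstable the cut is. It evaluates the same two-group model, so it cannot recover information within the groups or a shape that one step cannot express.

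**The case against.** **The wording is conditional.** The sentence sets a validation rule for any cutpoint that is used, and nothing in the SAP forbids a transformation. This stands: a reader might infer that every failing predictor must be cut, and the SAP does not say so. What remains is that no other remedy is named.

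**The SAP partly handles the problem.** Cutpoints go through the same resamples as the model, which covers the best-known harm of a data-driven cut, and variables are also used as continuous. The first part is a real strength. The second does not help once the linear term has failed.

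**The loss is easy to exaggerate.** This also stands. A cut at the 85th percentile gives a C-index of only 0.55 to 0.63 on the inputs of step 2, but nothing in the SAP selects such a cut. For a U-shape, values below 0.50 arise only if the direction of the cut is fixed in advance; a fitted coefficient can change sign. Nothing in the SAP suggests that any candidate has a U-shaped effect, so that case is a hypothetical.

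**Added value of RHC or cMRI.** A reader might infer that cutting natriuretic peptide or walk distance leaves residual confounding and so overstates what RHC or cMRI adds. The SAP does not support this as a finding. The dichotomisation rule stands under secondary objective 3, while the C-index and NRI comparisons belong to objectives 1 and 2, where no such rule is stated. The RHC and cMRI definitions used first there are themselves dichotomous, and their continuous measures would face the same rule, so the net direction is not established. It is a possible consequence only if the rule is carried over to the adjustment covariates.

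**A points score needs categories in the end.** True, but they are needed when the fitted model is turned into points, not when it is fitted.

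**Conclusion.** The point holds for the secondary objective 3 model and score. Dichotomisation is the only remedy named for failed log-linearity, and it is an inefficient one. On the assumed inputs a median cut keeps about 64% of the information, a well-placed cut costs about 0.03 to 0.07 in C-index for a monotone effect, and a U-shape, if present, would be largely missed.

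These sizes rest on a single normal predictor, the chosen shapes and about 35% events. In a model with several correlated predictors the change in overall C-index may differ. The loss of information under a cut does not depend on those choices.

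The primary sensitivity and specificity analysis does not use this rule and is unaffected. The change is worth making before the score is built, but it does not put the study's main result in doubt.

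**What to change.** Replace the sentence on dichotomisation under *Secondary objective 3* with a rule along these lines:

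- A continuous predictor that fails log-linearity is log-transformed if skewed, or otherwise entered as a restricted cubic spline with 3 to 4 knots at fixed percentiles.
- That step, including the decision to take it, is repeated inside each bootstrap resample with the variable selection.
- Cutpoints are used only when the fitted model is converted into score points.

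State also whether the same rule governs the adjustment covariates in the objective 1 and 2 models. This would settle the possible carry-over to the C-index and NRI comparisons.

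The cost is SAP wording. A log transform uses no extra degrees of freedom. A 3-knot spline uses 1 more than a linear term and a 4-knot spline 2 more. The results table becomes less simple, because a splined effect needs a plot or contrasts between chosen values instead of one hazard ratio.

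### The SAP does not extend its bootstrap validation to the additional cutpoints chosen by maximising the C-index, so as written their C-index is biased upward

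*SAP*

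**What the plan says.** The relevant text is the paragraph on internal validation in SAP section IV, Secondary objective 3. It makes four statements in this order.

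1. On the model and score: "Internal validation of the multivariable model and of the score which could be derived from it will be performed using the bootstrap method".
2. On the form of the variables: "variables will be used both as dichotomized variables (using the cut-offs used in the primary objective) and as continuous variables".
3. On one kind of derived cutpoint: "In case a continuous variable should be dichotomized for lack of log-linearity, the cutpoint will be validated in the same bootstrap resamples", these being the resamples used for the model and score.
4. As a further step: "optimal cutpoints will also be assessed on the continuous variables based on C-index maximization". A reference on cutpoint estimation with censored data is cited for it.

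Two other places bear on this. The part on proportional hazard analysis, under Secondary objectives 1 and 2, makes the C-index (with the NRI) the measure of predictive value. Section I sets a general two-sided 0.05 level for the whole plan.

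**The concern.** The third statement attaches validation to one trigger, lack of log-linearity. The fourth is introduced as an addition, covers the continuous variables without that trigger, and mentions no resampling, correction or exploratory status. Read as written, a cutpoint found by the fourth statement can be reported with its apparent C-index.

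That value is the maximum over many candidate cuts, so it overstates performance in new patients. The list of candidates is long: cardiac index, right atrial pressure, RVEF, stroke volume indices, pulmonary pressure and resistance, SvO2, compliance and right ventricular volumes, measured at baseline and at 3-6 months. The same paragraph also uses the fixed cut-offs of the primary objective. Within the search range, a maximised cut has an apparent C-index at least as high as any fixed cut, so an uncorrected comparison favours the new threshold by construction.

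**Working it through.** The SAP states no sample size, event count or power, so there is no figure of its own to reproduce. The check is a simulation of the procedure on a variable that carries no information.

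**Inputs from the SAP:** cutpoint chosen by maximising the C-index (Secondary objective 3); two-sided 0.05 level (section I).

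**Assumed:** number of patients n, proportion e with an event, exponential event times with censoring at 2 years, and the search range. The marker is normal and independent of outcome.

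**Formulas**
- Hazard: h = −ln(1 − e)/2. For e = 0.20, 0.30 and 0.40 this gives 0.112, 0.178 and 0.255 per year.
- C-index of a split: C = 0.5 + 0.5 × (concordant − discordant)/(comparable pairs).
- Selected cut: the one with the largest |C − 0.5| among 41 candidate quantiles, either direction allowed. Apparent C = 0.5 + |C − 0.5|.
- Optimism: in each bootstrap resample, repeat the search, then subtract the C-index of that cut in the original data from its C-index in the resample. Average over resamples. Corrected C = apparent C − optimism.

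There were 2000 data sets per row. The correction used 60 resamples in the first 150 data sets (100 for the two rows with e = 30%). The last column shows the mean apparent and corrected C in that subset.

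| n | e | Expected events | Search (percentiles) | Mean apparent C | 95th percentile of C | p<0.05 at selected cut | p<0.05 at median | Subset: apparent → corrected |
|---|---|---|---|---|---|---|---|---|
| 100 | 20% | 20 | 10-90 | 0.592 | 0.645 | 34.5% | 4.7% | 0.590 → 0.528 |
| 100 | 40% | 40 | 10-90 | 0.564 | 0.604 | 32.7% | 5.1% | 0.563 → 0.517 |
| 180 | 20% | 36 | 10-90 | 0.566 | 0.608 | 32.1% | 4.4% | 0.568 → 0.522 |
| 180 | 40% | 72 | 10-90 | 0.547 | 0.575 | 30.6% | 4.0% | 0.547 → 0.513 |
| 300 | 20% | 60 | 10-90 | 0.551 | 0.584 | 34.8% | 4.3% | 0.553 → 0.517 |
| 300 | 40% | 120 | 10-90 | 0.536 | 0.558 | 30.4% | 4.8% | 0.534 → 0.507 |
| 180 | 30% | 54 | 5-95 | 0.554 | 0.589 | 33.2% | 4.8% | 0.550 → 0.510 |
| 180 | 30% | 54 | 25-75 | 0.553 | 0.589 | 24.4% | 4.5% | 0.555 → 0.520 |

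**Effect of the grid.** A second set used n = 150, 200 and 300 with 0.18 events per year over 2 years. The event proportion is 1 − exp(−0.36) = 0.302, giving about 45, 60 and 91 events. Mean apparent C was 0.54 to 0.56. The share with log-rank p < 0.05 at the selected cut was:
- 38 to 40% when every observed value from the 10th to the 90th percentile was a candidate;
- 32 to 35% on the 41-point grid over the same range;
- 26 to 29% over the 25th to 75th percentiles;
- 4 to 5% at a fixed median cut.

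**Reading the results.** The excess of the apparent C-index over 0.50 runs from 0.036 to 0.092 and is largest with few events. Repeating the search inside the bootstrap removes most of it. At n = 180 with 20% events, (0.568 − 0.522)/(0.568 − 0.500) = 0.046/0.068, or about 68%. Across all rows the share is about 64 to 80%. The correction is therefore worthwhile but not complete.

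**The case against.** The strongest reply is that the paragraph already contains the remedy. It bootstraps the model and score, and it validates a cutpoint forced by non-log-linearity in the same resamples. C-index maximisation is the only data-driven cutpoint method that the SAP names. Where it supplies a log-linearity cutpoint, validation is already required. This stands in part: a reader might infer that the SAP rules out correction of the additional cutpoints, and it does not. It is silent. But the final sentence is worded as a further analysis without the log-linearity condition, and covering it by the preceding sentence means adding words. Nor does the bootstrap of the model and score settle the matter, because the SAP does not say that the additional cutpoints enter either. Nothing in the SAP says that the cited cutpoint method brings a correction with it.

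A second reply is that no test is planned at the selected cut. That is correct. A reader might infer from the general 0.05 level that p-values or hazard ratios will be given there, but the sentence plans none. The 25 to 40% figure is therefore conditional on someone reporting such a p-value. The bias in the C-index needs no such condition.

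A third reply is that no rule lets an optimal cutpoint replace a fixed one. That also stands: variables are still to be analysed continuously and at the primary-objective cut-offs.

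**Conclusion.** The gap is real but limited. The SAP states validation for one kind of data-derived cutpoint and does not extend it to the other. Followed as written, it yields an upward-biased C-index for the additional cutpoints: for a variable with no prognostic value, a mean of about 0.54 to 0.59 instead of 0.50. A log-rank p-value at the selected cut, if reported, would fall below 0.05 in roughly 25 to 40% of null variables, against 4 to 5% at a fixed median cut.

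These figures rest on assumed sample sizes of 100 to 300, event proportions of 20 to 40% over 2 years, and assumed search ranges and grids. The direction was the same in every scenario.

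Two stronger readings are not supported. One is that every uninformative variable would appear prognostic: at 25 to 40%, most would not reach nominal significance, although their apparent C-index would still tend to exceed 0.50. The other is that the main result is at risk: the primary sensitivity and specificity analysis uses fixed cut-offs and is unaffected. This is a supplementary step within a secondary objective. It is worth correcting because the C-index is the plan's own measure of predictive value.

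**What to change.** Extend the existing validation sentence in Secondary objective 3 so that it covers both kinds of cutpoint:

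- Repeat the C-index cutpoint search in every bootstrap resample already planned for the model and score.
- Report the optimism-corrected C-index and a bootstrap interval for the cutpoint.
- Compare the selected cutpoint with the fixed cut-off on corrected values only.
- Give no unadjusted p-value or hazard ratio at the selected cut.

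The search range should be stated too, since the nominal error rate depends on it. If the sponsor always meant the validation to cover these cutpoints, the change only makes that explicit.

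The cost is a short addition to the text and some computing time. The downside is a slightly less favourable reported C-index. Because some optimism remains after correction, the text should not present the corrected value as free of bias.

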However, by nature, 3 tests will be performed for each subject unless they experience death or are unable to perform one (or more) test during the follow-up. The repeated nature of the data will be considered including a random effect in the analyses. We will construct a logistic regression model with hemodynamic criteria for intermediate risk or high-risk status as outcome and cMRI dichotomous variable as exposure using a random effect at the patient level (2). The glmer command from the lme4 package will be used (R package, CRAN). Sensitivity and specificity and their confidence interval will then be extracted from the logistic model.

This analysis will consequently provide the overall (i.e. across the 3 time-points) sensitivity and specificity of cMRI integrated aforementioned exposition variable for the integrated aforementioned RHC definition taking into account the repeated nature of the data.

In addition, the following secondary analyses will be performed:

- sensitivity and specificity evaluation of cMRI integrated exposition variable for the integrated RHC at each time points (i.e. at baseline, 3-6 months and 24 months),
- sensitivity and specificity evaluation for each component of the RHC definition (i.e. considering only cardiac index $< 2.5 \text{ l/min/m}^2$ or only right atrial pressure $> \text{ or } = 8 \text{ mm Hg}$) and cMRI definition (i.e. considering only cMRI CI $< 2.5 \text{ l/min/m}^2$ or only RVEF $< 35\%$ or only absolute decrease of 10% of RVEF at a follow-up evaluation) overall and at each time-points.

In addition, parametric or non-parametric correlation analyses (depending on variable distributions) will also be performed for cMRI CI and RHC CI.

IV/ Analyses of Secondary objectives

Secondary objectives 1 and 2:

- 1) To assess the predictive value of the first occurrence of morbimortality events in 2 different analyses derived from RHC criteria (cardiac index (CI) $< 2.5 \text{ l/min/m}^2$ or a right atrial pressure $= \text{ or } > 8 \text{ mm Hg}$) and from cMRI criteria (CI $< 2.5 \text{ l/min/m}^2$ or RVEF $< 35\%$ or an absolute decrease of 10% of RVEF at a follow-up evaluation).
- 2) To assess the univariable association between first morbimortality events occurrence and NYHA functional class, 6-minute walk distance, plasma level of BNP/NT-proBNP, and continuous hemodynamic variables from cMRI, RHC and echocardiography data collected at baseline and after 3-6 months of follow-up.

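### Complications of cMRI and RHC are compared with an independent-samples chi-square although the same patients have both procedures; McNemar is only added alongside, with its unit of analysis unstated

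*SAP*

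**What the plan says.** Under secondary objective 4 in SAP section IV, the analysis of complications is presented as largely descriptive. Two formal comparisons are nevertheless planned. Overall adverse event and severe adverse event frequencies are to be "compared between groups using the Chi-Square test", with Fisher's exact test as the alternative. Then, "to account for the paired nature of the data, a McNemar test will be performed". The second is introduced as an addition to the first. The SAP does not say which p-value is the reported one, or whether a McNemar pair is a patient or a visit.

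The design is set out elsewhere in the SAP. Secondary objective 6 states: "This study is a prospective cohort study". Section III states: "There will be 3 time-points: baseline, between 3 and 6 months and 24 months", and that "3 tests will be performed for each subject unless they experience death or are unable to perform one (or more) test". Because section III judges cMRI against RHC at those time-points, both procedures are done in the same patients. For that primary analysis, "The repeated nature of the data will be considered including a random effect in the analyses". Objective 4 has no counterpart to this. Section I sets a two-sided 0.05 level for the SAP as a whole.

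**The concern.** Chi-square and Fisher tests compare two independent samples. Here the two sets of complications come from the same people, as the SAP's own next sentence acknowledges. A test whose assumption is known to fail should not be named first and then left standing beside the paired test.

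Two things are at stake. First, if patients prone to complications with one procedure are also prone with the other, the unpaired test overstates the standard error and can miss a real difference between the procedures. Second, two tests on two outcomes (adverse events, severe adverse events) give 2 × 2 = 4 p-values. With no rule on which test is reported, the choice could be made after the results are seen. The unstated unit for McNemar adds a further choice, because up to three visits per patient can either be collapsed or pooled.

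**Working it through.** The SAP gives no complication rate, event count or power figure for objective 4, so there is no stated number to reproduce. The check asks how far each test departs from its nominal level when the two procedures carry equal risk.

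**Inputs from the SAP.** Two-sided alpha 0.05 (section I); three time-points per patient (section III); both procedures in the same cohort.

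**Assumed inputs, none from the SAP.** 150 or 300 patients; complication risk per procedure 3%, 10% or 25%; three cMRI/RHC pairs per patient; a logistic-normal model. That model has a patient effect shared by both procedures and a separate patient-by-procedure effect, with SDs on the logit scale.

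**Step 1: chi-square with one pair per patient.** With risk p, n patients and correlation ρ between the two procedures, the variance of the difference is 2p(1−p)(1−ρ)/n. The chi-square uses 2p(1−p)/n. The true type I error is therefore 2[1 − Φ(1.96/√(1−ρ))]:
- ρ = 0.1: 1.96/√0.9 = 2.07, giving 3.9%.
- ρ = 0.5: 1.96/√0.5 = 2.77, giving 0.6%.

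This formula ignores the three visits, hence the simulation in step 3.

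**Step 2: McNemar on pooled visits.** Let d be +1, −1 or 0 for each visit (complication only with RHC, only with cMRI, or concordant). McNemar treats the d values as uncorrelated. With only a shared patient effect and equal risks, each patient's discordant pairs split 50:50, so d has mean zero within each patient and is uncorrelated across visits. The level then holds. If patients differ in relative propensity, a patient's d has its own non-zero mean, d is positively correlated across visits, and the test is inflated.

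**Step 3: simulation.** There were 6000 replicates per scenario. The Monte Carlo standard error near 0.05 is √(0.05 × 0.95/6000) = 0.0028. Each range covers the six combinations of patient number and risk.

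| Shared SD / patient-by-procedure SD | Chi-square, pooled procedures | Chi-square, any event per patient | McNemar, pooled pairs | McNemar, one pair per patient |
|---|---|---|---|---|
| 0 / 0 | 0.047–0.053 | 0.045–0.054 | 0.049–0.052 | 0.047–0.053 |
| 1.5 / 0 | 0.022–0.038 | 0.014–0.028 | 0.048–0.051 | 0.044–0.054 |
| 1.0 / 1.0 | 0.052–0.069 | 0.032–0.042 | 0.060–0.089 | 0.046–0.048 |
| 0.5 / 2.0 | 0.094–0.140 | 0.046–0.051 | 0.094–0.140 | 0.047–0.053 |

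Fisher's test was not simulated; it rests on the same independence assumption.

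**Step 4: candidate replacements.** Across all scenarios, the exact McNemar on one pair per patient gave 0.027–0.042. A patient-clustered paired test, (ΣDᵢ)²/ΣDᵢ² with Dᵢ the patient's sum of d, gave 0.046–0.054.

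**Step 5: dependence on risk.** In the shared-effect scenario, the patient-level chi-square gave 0.026–0.028 at 3% risk and 0.014–0.016 at 25%. The distortion is smaller when complications are rare, but not absent.

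**The case against.** The SAP sees the pairing and adds McNemar for it. It speaks of overall event frequency, which can be read as one pair per patient (any complication with cMRI against any with RHC). On that reading McNemar is valid, and the step 3 results bear this out. The analysis is also largely descriptive, and no decision rule in the SAP depends on these p-values. All of this stands and limits the severity. It does not justify keeping the unpaired test, and it does not tell the analyst which unit to use.

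A reader might go further and infer that both p-values are mis-calibrated because up to three pairs come from each patient. The SAP does not support that: it never says visits enter McNemar as separate pairs. Even if they did, repetition alone does not inflate the test. One might apply a design effect 1 + (3 − 1)ρ with ρ = 0.1, 0.3 or 0.5 as the correlation of discordance, and obtain 7.4%, 12.1% and 16.6%. The relevant correlation is that of the signed differences. In a separate simulation of 200 patients with a shared effect only, discordance correlated at 0.13 to 0.23 while the signed correlation was about zero. The formula would have predicted roughly 8% to 10%; pooled McNemar gave 4.7% to 5.3%.

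Nor do the two tests err in opposite directions as a rule. With large patient-by-procedure variation, both pooled tests are inflated over the same range.

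**Conclusion.** Wrong as written, minor severity. The chi-square/Fisher comparison contradicts the design, and the SAP's own next sentence concedes the pairing. Under a shared patient effect of SD 1.5 its type I error was about 0.014 to 0.038 instead of 0.05. It was calibrated when there was no within-patient correlation, and inflated on pooled procedures when patient-by-procedure variation was large. The McNemar part is a gap in specification, not a demonstrated error: one pair per patient is valid, and pooling visits inflates the test (about 0.06 to 0.14) only if patients differ in relative propensity to cMRI and RHC complications.

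All these sizes rest on assumed patient numbers, risks and variances. A reader might also infer that this comparison supports replacing RHC by cMRI. The SAP does not say so; its stated aim is the sensitivity and specificity of cMRI.

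**What to change.** In SAP section IV, secondary objective 4:

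1. Delete the chi-square/Fisher comparison.
2. Name one reported test and its unit: an exact McNemar test with one pair per patient, contrasting any complication with cMRI against any with RHC, over visits at which both procedures were done. Apply it to adverse events and to severe adverse events.
3. If visits are to stay separate, use a patient-clustered paired test instead, such as the one in step 4 above.
4. Report the paired risk difference, (patients with a complication only with RHC − patients with one only with cMRI)/patients analysed, with a 95% interval suited to paired proportions.

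The cost is a few lines of SAP wording and no new data. The exact patient-level test is slightly conservative (0.027–0.042 in the simulations) and loses per-visit detail, which descriptive counts by visit can supply.
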